7. TREATMENT PLAN

Duration of Study Treatment – 12 Months (330-420 days).

All subjects will receive the investigator standard postoperative regimen for cataract surgery. The retinal status of the subject will be monitored with a co-managing retinal specialist throughout the course of the trial.

8. EYE TO BE TREATED

If both eyes are eligible for the procedure, the study eye should be chosen based on the least amount of potential risk (i.e., the study eye that has the worse degree of pathology). If the level of pathology is the same OU, the non-dominant eye will be implanted.

9. ASSESSMENT FOR CAPSULAR STABILITY

Assessment for capsular stability will be performed preoperatively, intraoperatively and postoperatively.

10. OPHTHALMIC VISCO-SURGICAL DEVICE (OVD)

ProVisc® (sodium hyaluronate) Alcon, will be used as a surgical aid when inserting the IOPCL AMD MAG.

11. POSITION OF PCIOL HAPTICS AND IOPCL INCISION LOCATION

After adequate dilation, the surgeon will determine and record the orientation and angular dimensions of the haptics of the in-place PCIOL. The surgeon will also determine the degree and angular dimensions of the anterior capsule coverage in the planned region of the tri-haptic tunnel formation. The surgeon will determine if there is adequate coverage of the anterior leaflet capsule at the edge of the underlying PCIOL where the haptics of the IOPCL will reside. Adequate coverage is defined as greater than or equal to 0.5 mm of anterior leaflet of capsule above where the haptics will reside.

These notations will be transferred to the Pre-Operative case report form to document the position of the PCIOL haptics and IOPCL incision location.

12. SURGICAL TECHNIQUE: INSERTION AND REMOVAL INSTRUCTIONS

Video recordings will be created for each subject surgery and provided to the Sponsor for future review and assessment. **Prior to recording the case, please ensure that the video equipment is in full working order**. Video recordings will be shared with the FDA.

Any deviations from the surgical techniques described in the following sections should be captured as protocol deviations.

The Intraocular Pseudophakic Contact Lens (IOPCL) AMD-MAG is designed to improve near vision in the pseudophakic eye with AMD. Using a novel tripod haptic design (see figure 1) placed within 3 channels created under the anterior leaflet of the capsular bag, the optic is designed to self-center, secured over the existing posterior chamber intraocular lens (PCIOL). Each haptic has a ridge that acts as a pawl on the bottom that catches and locks onto the PCIOL optic edge. This pawl aids in both centering the IOPCL on the PCIOL optic as well as securely seat the haptic while contained under the anterior leaflet of the capsular bag. The lens is 4.5mm in diameter with the 3 extending haptics arranged in an isosceles pattern to avoid interference with the haptic/optic junctions of the existing PCIOL. The apex and leading tab are marked R to identify the anterior surface of the lens and prevent inverse implantation and help guide positioning onto the existing PCIOL. When the lens is right-side up the R should be visible and properly oriented when implanting the IOPCL.

Figure 1 - IOPCL AMD-MAG

[figure not shown]
12.1. Instructions for Use

12.1.1. Access to the Anterior Chamber

1. Mark the comea with provided comea marker, isolating the leading haptic mark. The leading haptic mark is to be placed on a lone side of the underlying PCIOL separated by the optic-haptic junction. The projected markings are to help guide the surgeon as to where the 1.5 anterior leaflet channel and partially dissected area of the anterior leaflet will be created to receive the IOPCL AMD-MAG haptic system.

Under sterile technique create a 2.75 mm wide beveled, self-sealing incision from the clear corneal limbus into the anterior chamber directly across from the planned placement of the leading haptic (denoted with the "R" inversion mark). Construct a 1.5 mm paracentesis directly across from initial 2.75 mm incision, with option (Surgeon preference) to create an additional paracentesis in any chosen plane to aid in IOPCL AMD-MAG positioning. The IOPCL AMD-MAG should be free from interfering with the optic-haptic junctions of the already seated in-the-bag PCIOL.

Figure 2 - ALIGNMENT OF THE IOPCL AMD-MAG IOPCL ALIGNED TO IOL IN CONTACT VERTICALLY

12.1.2. Assessment for Capsular Stability

With ProVisc in the anterior chamber using the Capsule Separator, enter the anterior chamber through the initial 2.75 mm incision. Prior to proceeding with anterior capsule dissection, confirm that the capsule is stable. Using the capsule separator, exert gentle downward force at each quadrant of the capsule aligned with the corneal mark to confirm that pseudophakodonesis is not present and that the capsule has minimal movement. If mobility of the lens/bag complex is too great that dissection cannot be performed without significant displacement of the lens/bag complex, the procedure should be aborted to avoid further stress on the zonules that may compromise the future stability of the lens/bag complex. If dissection can be performed without undue deformation of the lens/bag complex, continue with the procedure. Once again, introduce spatula through initial 2.75 mm main incision and cross iris plane in preparation to create an approximate 1.5 mm tunnel under the anterior leaflet of the capsule at leading haptic mark.

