5.2. Exclusion Criteria

- 1. Subjects who have already had cataract surgery with a toric or multifocal or accommodating Intraocular Lens.
- 2. Subjects who have already had cataract surgery with an Alcon SN60WF, SA60AT or SA60WF monofocal intraocular lens with a power below 17.0 diopters and greater than 24.0 diopters.
- 3. Subjects with non-stable neovascular (wet) AMD who received treatment within the past 12-months.
- 4. Subjects who have had a Nd: YAG capsulotomy less than 1 month prior to the planned date of the IOPCL surgery.
 - 5. Subjects who were treated with an PCIOL off-label.
 - 6. Subjects who have more than 1.0D of corneal cylinder determined by keratometry readings.
 - 7. Subjects whose continuous curvilinear capsulorhexis was less than 5mm or more than 6.0 mm in size at the time of PCIOL surgery.
 - 8. Subjects who had cataract surgery less than 6 months from the planned date of the IOPCL surgery.
 - 9. Subjects with anterior capsule fibrosis and phimosis that in the opinion of the investigator may confound the outcome or increase the risk to the subject.
 - 10. Subjects with capsular instability.
 - 11. Subjects with an anterior capsule defect.
 - 12. Subjects with posterior capsular defect (caused by Nd:YAG capsulotomy) extending toward the equator.
 - 13. Subjects who do not gain at least 10 letters of near visual acuity with the simulation/tolerance testing (using manifest refraction with +7.0D add) compared to conventional near vision testing (using manifest refraction with +3.0D add).
 - 14. Subjects with a concomitant retinal or choroidal disorder other than AMD.
 - 15. Subjects with any corneal abnormality, other than regular corneal astigmatism that in the opinion of the investigator would confound the outcome(s) of the study.
 - 16. Subjects with clinically severe corneal dystrophy (e.g., epithelial, stromal, or endothelial dystrophy).

- 17. Subjects with microphthalmos.
- 18. Subjects with a previous retinal detachment.
- 19. Subjects with a recurrent severe anterior or posterior segment inflammation of unknown etiology.
- 20. Subjects with iris neovascularization.
- 21. Subjects with glaucoma.
- 22. Subjects with advanced visual field defects (e.g., central large scotoma where magnification would not help).
- 23. Subjects with a fundus not visible.
- 24. Subjects with aniridia.
- 25. Subjects with advanced optic nerve atrophy.
- 26. Subjects with damaged or incomplete zonules.

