the edge of the underlying PCIOL. Confirm the capsule is stable by applying gentle pressure to all three seated haptic. If capsular stability is not confirmed, the IOPCL AMD-MAG should be removed (refer to Section 12.1.7 for removal instructions). Once stability is confirmed, perform thorough irrigation/aspiration of OVD and any displaced cortical material.

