16.3. Postoperative Ocular Adverse Events

Endophthalmitis

- Toxic Anterior Segment Syndrome (TASS)
- Chronic Anterior Uveitis
- Hyphema
- Hypopyon
- Implantable Pseudophakic Contact Lens Dislocation
- Cystoid Macular Edema
 - Clinically Significant Cystoid Macular Edema with reduction in BCDVA of 20/40 or worse at Form 3 (1-2 months post op) or later
- Pupillary Block
- Mechanical Pupillary Block
- Retinal Detachment
 - Rhegmatogenous Retinal Detachment
- Malpositioned/Misaligned Optics (IOPCL not centered over PCIOL and with unequal leaflet coverage of all IOPCL haptic tabs, or IOPCL tilted away from the PCIOL and without anterior leaflet coverage)
 - Early onset: occurring prior to Form 4 visit window (i.e., < 120 days)
 - o Late onset: occurring \ge 120 days
- Unseated IOPCL haptic tabs (One or more haptic tabs not securely attached to the PCIOL)
- Lens Optical Performance
- Mechanical Failure (Tear in haptic tab)
- Vitreous Aspiration for Pupillary Block
- Corneal Stroma Edema
 - o Corneal Edema with BCDVA of 20/40 or worse at Form 3 (1-2M post-op) or later
- Iritis present at 1-month or later
- Macular Edema present at 1-month or later
- Raised IOP requiring treatment
 - o Raised IOP, greater than 10 mmHg above baseline or greater than or equal to 25 mmHg.
- Iris Chafing
- Iris Trauma
- Iris Transillumination Defects

- Pigment Dispersion
- Pseudophacodonesis or Evidence of Zonular Trauma/Dehiscence
- Inter-device opacification or fibrosis between the PCIOL and IOPCL
- Ruptured capsular tissue
- Patient Reported Symptoms described as severe.
- Inability to go down steps, stairs or curbs in dim light or at night due to postoperative vision
- Inability to notice objects in the periphery while walking due to postoperative vision
- Other

Note: Secondary Surgical Intervention(s) (SSI) may be necessary to resolve any of the adverse events identified above. If an SSI is conducted in the trial, the details of the SSI and corresponding reason for SSI will be documented on the SSI CRF.

Examples of Secondary Surgical Interventions

- Irrigation of IOPCL/PCIOL Interface
- IOPCL Exchange
- Reposition of the same Implantable Pseudophakic Contact Lens
- IOPCL Removal
- Iridectomy for Pupillary Block

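### Protocol 12.1.2 gives conflicting go/no-go standards for a mobile lens/bag complex, and neither exclusion 10 nor the 12.1.4 removal rule is tied to them

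*Protocol*

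**What the plan says.** Capsular stability appears at five points in the protocol.

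- **Entry (5.2).** Exclusion 10 reads "Subjects with capsular instability", with no grade or test. Exclusion 26 separately bars "Subjects with damaged or incomplete zonules".
- **Timing (9).** "Assessment for capsular stability will be performed preoperatively, intraoperatively and postoperatively". The section gives no method or threshold.
- **Before dissection (12.1.2).** Pressing gently with the capsule separator, the surgeon is to "confirm that pseudophakodonesis is not present and that the capsule has minimal movement". The procedure is aborted if the complex is so mobile that dissection would displace it significantly. Otherwise: "If dissection can be performed without undue deformation of the lens/bag complex, continue with the procedure".
- **After seating (12.1.4).** The surgeon presses gently on the three seated haptics. "If capsular stability is not confirmed, the IOPCL AMD-MAG should be removed".
- **After surgery (16.3).** "Pseudophacodonesis or Evidence of Zonular Trauma/Dehiscence" is a listed postoperative adverse event, with no reference to the preoperative finding.

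Section 17 records adverse experiences whatever their cause. SAP 7.5.6 counts eyes with each event by visit and over the study. Section 15 schedules a capsular stability assessment preoperatively, operatively and at each visit from 7-14 days. Section 12 requires any departure from the surgical technique to be captured as a protocol deviation.

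**The concern.** This is the step that decides whether an eye receives the device. A surgeon who finds some pseudophakodonesis in an eye that can still be dissected gets two answers from one paragraph. That paragraph explains that aborting is meant to spare the zonules further stress. An eye passed by the looser sentence can nevertheless reach the removal rule after dissection and insertion have taken place.

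Three things are at stake: the subject's exposure to surgery, consistency between sites, and how the eye is reported. Section 2 plans three sites and chooses investigators with no surgical experience of this lens, so they have no practice with it from which to supply a shared threshold. Depending on the reading, the same eye could be screened out, recorded as a failure to implant (an intraoperative adverse event in 16.2), have the lens removed, or be implanted and later counted under postoperative pseudophakodonesis.

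**Working it through.** The plan states no figure on this point, so the check is mainly a comparison of text.

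**Step 1: the standards side by side.**

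| Place | Standard | Consequence | Threshold or definition |
|---|---|---|---|
| 5.2, exclusion 10 | capsular instability | not enrolled | none |
| 12.1.2, confirmation | no pseudophakodonesis, minimal movement | to be confirmed before dissection | none for minimal |
| 12.1.2, abort | dissection would displace the complex significantly | abort | none for significant |
| 12.1.2, continue | no undue deformation on dissection | continue | none for undue |
| 12.1.4 | stability not confirmed after seating | remove the device | none |

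**Step 2: a test case.** Take an eye with some pseudophakodonesis that can be dissected without significant displacement or undue deformation.

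- Confirmation sentence: not met, because pseudophakodonesis is present.
- Abort sentence: not triggered.
- Continue sentence: met, so the instruction is to go on.

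The confirmation and continue sentences therefore give opposite answers for the same eye at the same moment. The section names no action for an eye that fails confirmation but does not reach the abort trigger.

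**Step 3: deviations.** Under section 12, continuing departs from the confirmation sentence and stopping departs from the continue sentence. Either decision could be logged as a deviation, or neither.

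**Step 4: downstream.** The same eye may or may not satisfy 12.1.4, which does not say whether movement tolerated before dissection is acceptable after seating. If the device is removed at surgery, the eye stays in the SAP section 5 population, which includes attempted implantations. If the device stays in, mobility seen later meets the 16.3 event, and nothing in 16.3 or SAP 7.5.6 separates mobility already present from mobility that is new.

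**Step 5: scale.** SAP 6.2 caps the study at 10 eyes. One eye classed differently changes a rate by 1/n:

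- n = 10: 1/10 = 10.0 points. The observed rate is 0/10 (exact 95% interval 0% to 30.8%) or 1/10 (0.25% to 44.5%).
- n = 9: 1/9 = 11.1 points.

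Since n cannot exceed 10, the shift is at least 10 points. The intervals overlap heavily, so one eye does not change the inference much. It does change the count that is reported. The documents give no frequency of mobile but dissectable eyes, so the number affected cannot be estimated.

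**The case against.** The strongest reply is that checks at different stages should differ. Screening, instrument pressure before dissection and pressure on seated haptics are different tests, and the last can properly detect instability that surgery itself caused. This stands: continuing under 12.1.2 and then removing under 12.1.4 is not in itself a contradiction. It does not answer the conflict inside 12.1.2, where both standards apply at one stage.

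Several stronger readings are tempting but unsupported.

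- **That a mildly mobile eye must be excluded, or must have the device removed.** Exclusion 10 does not say that any degree of mobility counts, and 12.1.4 does not define failure to confirm. The text leaves both to judgement.
- **That the primary objective is compromised.** That objective (Protocol 4, SAP 2) concerns adherence of the IOPCL to the existing lens. Gap, tilt and decentration serve it, and none of these uses the capsular stability check.
- **That pre-existing mobility is declared to be implant harm.** No section attributes the event to the implant, and section 17 records events whatever their cause. The narrower point is that no rule separates old findings from new ones.
- **That such an eye is likely to occur.** An assumed frequency of 5% to 20% gives a chance of at least one in ten of 1 - 0.95^10 = 40% to 1 - 0.80^10 = 89%. The result only restates the assumption, and exclusions 10, 26 and 27 (pseudoexfoliation) should make such eyes less common.

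There are also existing controls. Surgeries are video-recorded for sponsor review. Appendix 3 and the case report forms, which are not in the text available here, may define the assessment. They could supply a method, but the sentences in 12.1.2 would still conflict.

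**Conclusion.** The point holds as an internal contradiction in 12.1.2, compounded by the lack of any link to exclusion 10 and to the 12.1.4 removal rule. It should be corrected because it sits at a go/no-go surgical step, bears on subject safety, and leaves deviations without a consistent classification.

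Its numerical reach is modest. Each affected eye moves a rate by at least 10 points, the number of such eyes is unknown, and the SAP is descriptive. The numerical suspension triggers in 4.2 concern severe ocular injury and explant for visual intolerance, so they do not turn on this classification.

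The conclusion rests on the wording of 12.1.2 and on no assumed frequency. It takes no view on which stability standard is clinically right.

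**What to change.** 1. **Protocol 12.1.2.** Reconcile the confirmation, abort and continue sentences, so that every finding leads to one stated action. The sponsor and investigators choose the criterion.
2. **Protocol 5.2 and 12.1.4.** Make exclusion 10 and the removal rule consistent with 12.1.2, stating the criterion for each stage. The tests may differ by stage; what is needed is that each is written down and its relation to the others is clear.
3. **Protocol 16.3 and SAP 7.5.6.** Keep recording and counting every postoperative pseudophakodonesis event. Add a tabulation of whether it was already present at the preoperative capsular stability assessment or is new or worse since then.

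The intraoperative finding should not serve as the baseline. Mobility caused by dissection or seating could be recorded at surgery, become the reference, and then be classed as pre-existing. Nor should the count be limited to new or worse cases, which would sit badly with section 17. The protocol already uses such references elsewhere: postoperative PCIOL tilt is compared with preoperative tilt in 4.1, and one raised-pressure limit in 16.3 is set against baseline.

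The cost is wording in three protocol sections, a line in the adverse event text and one extra table. No new assessment is needed, because section 15 already schedules the preoperative and postoperative ones. Depending on the criterion chosen, the number of eyes implanted may change slightly.

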12.1.3. Preparation of the Capsular Channels

Construct a liberal 1.5 mm size tunnel under the anterior leaflet of the capsule to house the leading haptic tab Note: The 'R' haptic is to be positioned between the two PCIOL haptics and the other two haptics on the other side between the two haptics markings, as shown in **Figure 2**. Using the lateral mark on the anterior surface of the spatula as a guide, advance the spatula beyond the edge of the PCIOL until the lateral mark is aligned with edge of the underlying PCIOL. Suggestion: Separate leading edge of anterior capsule approximately 2 mm either side of corneal marking to ease introduction of IOPCL haptic leading edge. Utilizing the paracentesis, introduce and advance the spatula across iris plane and create a sweeping dissection of anterior leaflet from the center of one corneal mark to the other. If cortical material is present, break up and remove any loose cortical material. Once again using the lateral mark on the anterior surface of the spatula as your guide, create a space approx. 2mm beyond the edge of the existing PCIOL to allow space for the tip of each IOPCL haptic to properly seat unrestricted beyond the optic edge of the existing PCIOL. To further dissect or elevate anterior leaflet from capsule, you may insert viscoelastic under the leading haptic tunnel and swept area of the anterior leaflet capsule.

12.1.4. Insertion of the IOPCL

Load the IOPCL into the LIOLI-22 injector according to the manufacturer's instructions.

CAUTION: It is important to place the IOPCL in the center of the cartridge chamber so that the haptics are well away from the edges of the flaps when they are folded closed. Otherwise, the haptics may get caught between the flaps and become torn when the plunger is pressed to advance the IOPCL AMD-MAG in the injector tip. It is also suggested that additional ProVisc be placed at the posterior entrance to the cartridge to provide a buffer between the plunger and the folded IOPCL AMD-MAG. Place additional viscoelastic on the surface center of the optic and while closing the cartridge press down on the center of the optic with IOL forceps to assure the haptics remain free of the cartridge flap. Once the cartridge is successfully closed, insert cartridge into provided slot of injector. Carefully push the plunger forward to ensure that the silicone tip correctly enters the loading chamber, while making sure not to capture one of the haptics between the plunger and the cartridge wall. Continue to push the tip until the inner spring begins to compress. Pull the plunger back a few millimeters and then push it forward again. This step ensures that the lens is advanced without restriction.

Through the previously placed 2.75 mm main cornea incision, inject the IOPCL AMD-MAG with the leading haptic forward denoted by the "R" inversion mark into the anterior chamber of the eye. Using an IOL manipulator, such as Sinskey or collar button, rotate the IOPCL AMD-MAG to line up the haptics with the previously created channels. Utilizing an IOL manipulator, introduce first the trailing haptics under the partially dissected area of the anterior leaflet assuring each haptic is seated properly and can grasp the edge of the IOL. Next, introduce the leading haptic into the previously created 1.5 mm anterior leaflet tunnel. If needed during the introduction of the haptic system, introduce a second instrument through paracentesis or the main incision to aid in lifting edge of capsule to ease the advancement of the IOPCL AMD-MAG haptic system under the anterior leaflet. After the placement of each haptic, confirm that it is beneath the anterior flap, properly seated and has captured the edge of the existing PCIOL. Finally, using light rocking motion, manipulate the IOPCL AMD-MAG to assure the tri-haptic system has a uniform grasp to

the edge of the underlying PCIOL. Confirm the capsule is stable by applying gentle pressure to all three seated haptic. If capsular stability is not confirmed, the IOPCL AMD-MAG should be removed (refer to Section 12.1.7 for removal instructions). Once stability is confirmed, perform thorough irrigation/aspiration of OVD and any displaced cortical material.

12.1.5. Ease of Handling Capsular Tissue during IOPCL implantation

The amount of difficulty handling the capsular tissue during IOPCL implantation and the operative date of the PCIOL procedure will be recorded on the operative form.

